3.0 METHODS

We have conceptualized our study, evaluating clinical care and outcomes of childhood nephrotic syndrome, based on Donabedian's well known 'structure, process, and outcome' framework for health services evaluation.⁵⁴ Our work plan to achieve objectives 1 and 2 (to evaluate association of steroid dose prescribed with outcomes, and to understand sources of variability in treatments), using both quantitative and qualitative methods and a nested data architecture with patients' data linked to their physicians and physicians' data linked to their centres (see adjacent figure), will broadly address structure, process and outcome elements operating at three levels. First in section 3.1 below, we provide details regarding creation and characterization of the prospective cohort – the means by which we will achieve objectives 1 and 2.

3.1 Cohort Creation and Characterization

Population and setting: All children who present to pediatric nephrology clinics with a clinical diagnosis of nephrotic syndrome will be eligible for enrollment into the longitudinal cohort. All pediatric nephrology centres in Canada (n=13) are participating in this national study (see attached support letters). All pediatric nephrologists who care for children with nephrotic syndrome in Canada are eligible for enrollment.

Enrollment period: The enrollment period for the prospective cohort will last 4.0 years. The observation period will continue for an additional 6 months after the enrollment period (to ensure minimum 6 months follow-up for all patients by end of study).

Inclusion criteria: A patient is eligible to enter the cohort if he/she meets one of the following 2 criteria. See Appendix, Figure 1 for patient enrollment plan.

- A child with **first presentation** of nephrotic syndrome who meets the following criteria: age 1 to ≤17.5 years; edema present; urinalysis shows proteinuria (> 3+ on dipstick; > 3 g/L on urinalysis or urine protein to creatinine ratio > 200 mg/mmol); serum albumin < 25 g/L; and no prior treatment with steroids.
- A child with an established diagnosis of childhood nephrotic syndrome who presents at the beginning of either a **first or second relapse** (defined as proteinuria > 3+ on dipstick, > 3g/L on urinalysis or urine protein to creatinine ratio > 200 mg/mmol for 3 consecutive days) during enrollment period, prior to start of steroid sparing agents or kidney biopsy.

[figure not shown]
Exclusion criteria: Patients will be excluded if they meet one of the following criteria either at enrollment or during course of study: 1) secondary cause of nephrotic syndrome (e.g. lupus, malignancy); 2) C3 low suggesting high likelihood of secondary cause of nephrotic syndrome. Patients ultimately shown to be steroid resistant will be excluded from the final analysis, but will continue to be followed in the prospective cohort. Enrolled patients who turn 18 years of age during the study will exit the study. Further follow-up will be sought for these adult patients using a revised ethics application.

Patient enrollment: Two team members from each participating site will be primary contacts for the study (one physician and one nurse/research staff). Every 2 weeks these individuals will generate a list of patients seen with nephrotic syndrome by reviewing inpatient and outpatient data (clinic scheduling records) to determine eligibility. All patients with a clinical diagnosis of nephrotic syndrome who meet the inclusion and exclusion criteria will be introduced to the study by the primary treating physician. The site investigator will approach patient/parents to obtain informed consent and will also obtain assent from older patients (age >12 years). Patients will be enrolled in the study if they meet inclusion criteria and

their legal guardian has given informed consent. Consent forms will be available in English and French. Logs of all patients screened and consented, and for those who declined the reason will be kept.

Physician enrollment: Informed consent will be obtained from physicians within participating nephrology care teams to allow their demographic information (age, gender, location of nephrology training, years in practice) to be collected. Physician data will be linked to their patient's data in the nested data architecture. Once linked, physician identifying information will be removed. If a consenting patient's physician declines to participate in the study, the patient's data will be linked to a generic category of 'unknown physician.'

Patient data being collected: Study data will be collected at the following study points (see Figure below and more details shown in Appendix, Figure 2): 1) study entry (whether first presentation, first relapse or second relapse); 2) at the beginning of all subsequent relapses [defined as proteinuria > 3+ on dipstick, > 3g/L on urinalysis or urine protein to creatinine ratio > 200 mg/mmol for 3 consecutive days or start of full dose steroids (60 mg/m² or 2mg/kg)]; 3) at the end of first presentation and end of all subsequent relapses [defined as both remission of proteinuria – negative or <1.0 g/L protein on dipstick for 3 consecutive days, and off steroids]; 4) study visits every 6 months after entry; 5) at start of all steroid sparing agents; 6) at time all kidney biopsies; and 7) study end.

At entry, we will record demographic information (age, gender, ethnicity, family income, parental education, past medical history), height, weight, blood pressure, blood test results (C3, albumin, cholesterol, creatinine), urine protein values by dipstick (routine clinical practice is to use urine albumin dipsticks [Albustix™, Bayer], but urine protein to creatinine ratio will be recorded if available), medical history and details of steroid prescription. For patients entering at first or second relapse, demographic and treatment information regarding first presentation and/or first relapse will be collected using retrospective chart review when available. We will allow for enrollment up to second relapse (lengthening time interval to obtain consent) in order to maximize patient recruitment. Standardized assessments by physicians will be performed at the following study points: study entry, semi-annual study visits, and at study end.

Data for study points will be obtained using one or all of the following methods: chart review, reviewing patient log books of daily home urine protein measurements and steroid dose given, and phone calls to family to confirm details of clinical course (including date of proteinuria remission for each relapse). Logs maintained by patients are part of routine clinical care in nephrotic syndrome; all study patients will be provided with standardized log books for medications and relapse tracking. This schedule and method of assessments for study points were designed to mirror routine clinical care (as reported by most sites) and to maximize feasibility while maintaining ongoing engagement by study patients and physicians.

Defining an episode of treatment: As nephrotic syndrome is a relapsing and remitting disease, a significant portion of the study data will involve documenting treatment for both first presentation and

relapses of nephrotic syndrome (called ‘episodes’ in this study). Detailed steroid prescription information will be recorded at entry, and at the beginning and end of all subsequent episodes.

An **episode** is defined as the time from start of full dose steroid therapy (60 mg/m² or 2mg/kg) to cessation of steroids or re-start of full dose steroids as in steroid dependent patients who relapse while tapering steroids.

The standard definitions used in nephrotic syndrome are provided in Appendix, Table 2. The data collection forms, shown in Appendix Figure 3, are designed to capture steroid prescriptions for each episode from the date of start of full dose steroid therapy (60 mg/m² or 2mg/kg) to cessation of steroid therapy or restart of full dose therapy. Each patient’s steroid prescription for an episode will be linked to the prescribing physician.

Data quality and standardization: Standardized case report forms will be used for data collection regarding the clinical course, outcomes and treatments for childhood nephrotic syndrome. All patient and physician data will be entered by study staff into a multi-centre online database (REDCap™, a web-application which allows users to build databases securely for the purposes of research and in particular for longitudinal cohort studies, <http://project-redcap.org/> hosted by Women and Children’s Research Institute, Edmonton, see letter from [name]). Data are being monitored weekly to address data quality issues in real-time. Based on the 77 subjects enrolled to date, we have confirmed that the majority of data to be collected for this study is recorded routinely by nursing staff in clinical care, and the web based system does not pose significant additional onerous data entry requirements.

The study will be coordinated centrally in Calgary. Two central study staff (study nurse and data analyst) will train all other site-specific study staff regarding study goals and objectives, data management and data entry. We put in place several measures to ensure data consistency and standardization including: piloting case report forms and standardizing forms; training site staff for data element definitions; using a data dictionary; establishing inter-rater reliability for data entry using two study staff at each site at start of study; and pre-study patient visit planning to standardize data collection and entry. Every 3 months, data analyst will review data entry completeness for individual patients and send reminders to appropriate site investigators for data completion. There will be a 2 step review for data completeness for each patient record – first by the data analyst and second by a lead investigator or designate. Data are time-stamped as complete after review. Key measures of data quality were identified a priori; a sample data quality report is attached in Appendix, Tables 3 and page 16.

Privacy and confidentiality: We will assign unique study numbers to patients, physicians and centres – to protect anonymity of all participants and centres. All identifying information will be securely stored at individual sites and will not be shared with central study staff.

Characterizing the cohort: We will describe (using means with standard deviation, medians with interquartile range and proportions as appropriate) the cohort demographics, and all outcomes of interest by centre-, physician, and patient- level variables. We will describe the following outcomes: overall steroid prescribed (total dose and number of treatment days), time to first relapse, relapse rate during observation, time to steroid sparing agents, choices of steroid sparing agents and indication, time to kidney biopsy, reasons for biopsy, complications of steroid therapy. Outcomes related to complications of steroid treatment will include: anthropometric changes during observation period (age- and sex-specific standard-deviation scores (z scores) for height, weight, and body-mass index); persistent systolic/diastolic blood pressure $\geq 95^{\text{th}}$ percentile during observation period [yes/no] and requirement for antihypertensive therapy [yes/no] and duration of therapy; and external manifestations of steroid toxicity evident during semi-annual study visits (Cushingoid faces [yes/no], hypertrichosis [yes/no], cataracts [yes/no], striae [yes/no], acne [yes/no]). Definitions of external manifestations of steroid toxicity are

similar to those observed in prior nephrotic syndrome steroid dosing studies.³⁸ See Appendix, Table 4 for detailed description of these variables.

3.2 Work plan for objective 1

Design: To determine the association of steroid dose prescribed with relapse rates, we will use the prospective cohort as described in section 3.1. We hypothesize that increasing steroid dose prescribed per unit time will be associated with decreasing relapse rates. All patients with steroid sensitive nephrotic syndrome enrolled into the prospective cohort will be eligible for this study. The observation period will span a maximum of 4 years and minimum of 6 months. Figure 4 in the Appendix provides a visual representation of the outcome and exposure as defined below for this objective.

Outcome: The primary outcome of interest is relapse rate (number of relapses/per person unit time). Relapse rate is the most clinically relevant outcome for nephrotic syndrome and the best indicator of morbidity experienced by patients; this outcome definition is consistent with prior literature in this area.⁴⁰

Exposure: The exposure is steroid prescribed per unit time - that is the total dose patients were prescribed as treatment for episodes of proteinuria divided by the sum of duration of 'days on steroids' during observation period. Days on steroids is defined by the sum of the length in days of all episodes (see definition of episode in section 3.1, also graphically represented in Appendix Figure 4) observed. This definition is consistent with measures of steroid exposure used in prior nephrotic syndrome steroid dosing studies conducted in Europe and in a Canadian study of steroid associated osteoporosis in children.^{38,55} Systemic steroid exposure (both oral and intravenous) will be converted into prednisone equivalents (mg/m^2) using standard dose conversion tables and weight based dosing criteria [mg/kg] will be converted to mg/m^2 .

Analysis plan: The unit of analysis is the patient. Given that the main outcome of interest is relapse rate, we will use Poisson regression models with steroid prescribed per unit time as the exposure and relapse rate per unit time as the outcome, adjusting for patient level variables (age, gender, ethnicity, household income, parental education) and episode at entry into study (either first presentation, first relapse or second relapse), and taking into account time at risk. We are not using multi-level (hierarchical) analysis in this objective, as there is no clustering at the patient-level. There is only one measurement per patient, relapse rate adding all episodes experienced by one patient as a count.

Feasible sample and power considerations: We estimated a feasible sample based on data gathered from 2 sources: an ongoing longitudinal study of children with nephrotic syndrome (INSIGHT study, led by [name]) recruiting a Toronto based cohort,⁵³ and our preliminary data (Appendix Figure 5 for preliminary recruitment rate). Based on the expected consent rate of 72%, and estimated drop out of 10% (due to loss to follow-up or steroid resistance), we estimate that we will be able to enrol and follow, at least, 520 patients over a period of 4.0 years (65 patients every 6 months). In our preliminary work, we have already enrolled 77 patients from 6 sites, thus our total estimated sample is 597 patients.

Although we hypothesize that increasing steroid dose prescribed per unit time will be associated with decreasing relapse rates, no studies to date have reported a specific magnitude of the effect of steroid prescribed per unit time on relapse rates. A systematic review of available clinical trials examining this issue, published in 2007, only reports on risk ratios based on the dichotomous outcome of any relapse at a pre-specified time interval (usually 12 or 24 months).⁴⁰ Our outcome of interest is an actual rate (count of relapses/person years). Hence, a power based, effect size dependent sample size calculation was not performed. At a significance level $\alpha = 0.05$, and under the following assumptions of a mean daily steroid dose of $30.64 \text{ mg}/\text{m}^2$ with a standard deviation (of the dose) of 8.85, a base rate of relapse of 1.68 per person year, average follow up (time at risk of relapse) of 2 years and a conservative correlation (R^2) of the steroid dose with other covariates of 0.2, we would have 90% power to detect an incidence rate

ratio of 0.989 or smaller (i.e. a larger effect size) in a multiple Poisson regression. We are allowing for a 2 tailed test to allow the possibility of the effect being on either side of the null.

3.3 Work Plan for Objective 2

Design: To determine the associations between centre-, physician-, patient-level characteristics and i) steroid dose prescribed, and ii) length of steroid treatment for first presentation and subsequent relapses of nephrotic syndrome, and to identify reasons for practice variation between and among pediatric nephrology care providers and centres, we will use a mixed methods approach as defined by Creswell & Plano Clark.⁵⁶ The primary study is a quantitative study using the prospective cohort as described. A qualitative study, serving a supplementary role, is embedded within the larger quantitative study to provide a deeper understanding of the complex multi-level processes that lead to practice variation between centres and between physicians within centres. True to qualitative approaches, no a priori hypothesis is specified for this aim. At the completion of quantitative and qualitative studies, we will use a convergent parallel mixed methods analytic approach (both quantitative and qualitative data collected and analysed during the same phase of research, then two sets of results are merged for an overall interpretation), to compare qualitative and quantitative data across centre-, physician- and patient-level attributes. The results of both components will inform the ‘greater whole’ - a comprehensive understanding of why there is variability in care for nephrotic syndrome – a key step to overcoming barriers to implementation of best practice approaches for treatment of nephrotic syndrome across Canada and to make future randomized controlled trials more feasible.

Description of the quantitative study: We will use the prospective cohort described in section 3.1 to determine the associations between centre-, physician-, patient-level characteristics and outcomes. All patients with steroid sensitive nephrotic syndrome and all physicians enrolled into the prospective cohort will be eligible for this study. We will use the hierarchical data in the prospective cohort. The observation period for this objective will be a maximum of 4.0 years and minimum of 6 months.

Outcomes: The primary outcome is steroid prescribed per episode. We will examine: a) total dose patients receive for an episode; and b) average daily dose by dividing the total dose by duration (in days) of the episode. Dose will always be in mg/m² prednisone equivalents. This outcome definition is consistent with measures of steroid exposure used in prior nephrotic syndrome steroid dosing studies.^{38,55} We are evaluating steroid prescription per episode because in this objective, we will study determinants of variability in steroid prescription for episodes of proteinuria rather than patient outcomes related to cumulative exposure of steroids (e.g. relapse rate). All episodes will be categorized either as first presentation or relapse. The secondary outcome will be length of episode in days.

Exposures: Exposure variables of interest are categorized into centre-, physician- and patient-level variables. Centre-level variable is defined as existence of a standardized protocol within centre for treating first presentation and relapses (information will be obtained from the site investigator as existence of centre based protocols [yes/no]). Physician-level variables are gender, year of graduation from nephrology fellowship, and location of nephrology training (Canada vs. outside Canada). These centre- and physician-level variables were shown to impact variability in practice patterns according to our published survey.²² Patient-level variables are age, gender, ethnicity, and status at entry into study (first presentation, relapse). These variables are further described in Appendix, Table 5.

Analysis plan: We will describe the primary and secondary outcomes according to each of centre-, physician- and patient-level characteristics with 95% confidence intervals. To study the associations of centre-, physician-, patient-level characteristics with the primary outcome (steroid prescribed per episode), we will use mixed effects models with fixed effects for centre (standardized protocols yes/no), physician (gender, years in practice, location of training), and patient (age, gender, ethnicity) characteristics and random effects to account for physicians clustering within centre, patients clustering

within physician, and episodes clustering within patients. We will create separate models to examine both total dose patients receive for the episode, and average daily dose by dividing the total dose by duration (in days) of the episode. The unit of analysis will be the episode. Each episode will be categorized as either first episode or relapse at the patient level in the same model. The same methodology will be used to study the length of episode in days (secondary outcome).

Description of the embedded qualitative study: The embedded qualitative study will enrich the quantitative results by providing detail regarding attitudes, beliefs and local factors driving variation in care - fundamental to understanding the complexity of health care professional decision-making.^{57,58} Theoretically grounded in the *Ottawa Model of Research Use*,⁵⁹ we are conducting focus groups with health professionals who care for children with nephrotic syndrome to probe the reasons for variation in steroid protocols ('why do people do what they do'). Ten focus groups, one per site with 6-8 participants per group and each lasting 60 minutes, are planned. Informed consent will be obtained and participant responses will be anonymized. We are not requesting funds from CIHR for this study as we have completed 8 of these 10 focus groups; however, we have provided the interview guide and the preliminary results in the Appendix (pages 22-24) - as it is a critical component of our mixed methods design and KT plan.

Integration of quantitative and qualitative studies: We will independently analyze the qualitative and quantitative data using analyses for Objective 2 as detailed above. We will use a convergent mixed methods analytic approach to compare the results obtained in the quantitative with qualitative components (Appendix Figure 6), using matrices of the hierarchies of centre-, physician- and patient-levels and explanatory quantitative variables at each level and themes related to these same levels arising from the qualitative study (e.g., existence of standardized protocols in each centre, age and training background of the physician, patient's age and ethnicity; Appendix Table 6), asking whether two types of data are congruent or not.

Feasible sample and power considerations: For objective 2, there is no knowledge on expected effects from the explanatory variables on the outcome. Therefore, power calculations, which are based on having a specific alternative hypothesis, are not feasible. The analysis to be performed is a mixed effects model with three random effects (physicians within centre, patients within physicians and episodes within patients), for which there is no simple analytic formula to calculate the needed sample size. The innovative method of Monte Carlo simulation based on the number of subjects potentially available still needs to have as input the expected effects from each of the explanatory variables. In the case of this linear mixed model (for primary outcome), the effect of each variable is measured by its coefficient in the regression (for fixed effects) and by the estimated variance of the random effects. As justified in Objective 1, we expect a feasible sample of 597 subjects. Given this estimated enrollment number, and that we will have a total of 8 explanatory variables plus 3 random effects (estimated as parameters in the model), we are complying with the guideline of 10 observations (at the unit of analysis level) per variable.⁶⁰ As the unit of analysis will be the episode and an estimated 70% of patients will have more than one episode during the study, it is important to note that the 597 patients will yield from 597 to 1015 observations (episode at entry plus one additional relapse). This will ensure that estimates of random effects are feasible.

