2.2 Steroids are the treatment of choice for first presentation and subsequent relapses of nephrotic syndrome. Clinical response to steroids is the most important predictor of disease course.² Steroid sensitive patients typically respond to treatment with remission of proteinuria within 2 weeks of therapy and maintain normal kidney function. Steroid resistant patients, defined as those who fail to achieve complete remission of proteinuria after 8 weeks of steroid therapy, have a high risk (>50% in 5 years) of kidney failure.^{32,33} Approximately 90% of children with nephrotic syndrome are steroid sensitive, and they will be the focus of our study.^{34,35} Among these patients remission is achievable with steroid treatment; however, relapses are common requiring multiple courses of steroids and steroid sparing immunosuppressive drugs - leading to significant side effects drug toxicity. Of the children who relapse, up to 50% will have frequent relapses (≥ 2 relapses within 6 months of first response or ≥ 4 relapses in any 12 month period) or become steroid dependent (2 consecutive relapses during tapering of steroid therapy, or relapse within 14 days of steroid cessation).^{10,30} Steroid toxicity reported in children with nephrotic syndrome includes growth retardation and obesity,^{7,9,13,36} hypertension,^{11,37} posterior sub-

capsular cataracts,^{6,12} decreased bone mineral density,^{14,15} and impaired glucose tolerance.⁸ Minimizing relapse rates and steroid exposure are the most important goals in caring for these patients and remain the most relevant clinical outcomes.

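### Excluding the whole child if steroid resistance is shown at any later time makes the analysis set depend on post-entry course and discards valid steroid-sensitive follow-up

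*Protocol*

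**What the plan says.** The exclusion criteria in Protocol section 3.1 end with this rule: "Patients ultimately shown to be steroid resistant will be excluded from the final analysis, but will continue to be followed in the prospective cohort". It acts on the patient, not the episode, and sets no time limit.

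Section 2.2 gives the definition: "Steroid resistant patients, defined as those who fail to achieve complete remission of proteinuria after 8 weeks of steroid therapy". It does not say that the 8 weeks must belong to the first course. Section 3.1 refers to standard definitions in Appendix Table 2, which is not shown.

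The target population is clear. Section 2.2 says: "Approximately 90% of children with nephrotic syndrome are steroid sensitive, and they will be the focus of our study". The Objective 1 design in section 3.2 says: "All patients with steroid sensitive nephrotic syndrome enrolled into the prospective cohort will be eligible for this study". Section 3.3 restricts Objective 2 in the same way.

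Entry is also open after the first course. Section 3.1 admits "A child with an established diagnosis of childhood nephrotic syndrome who presents at the beginning of either a first or second relapse".

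The Objective 1 analysis has one record per child: "There is only one measurement per patient, relapse rate adding all episodes experienced by one patient as a count". Nothing in the protocol says what becomes of follow-up accrued before resistance was declared.

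**The concern.** A relapse implies an earlier remission. Every child who enters at first or second relapse has therefore already responded once, and resistance declared in such a child is late. The same holds for a child who enters at first presentation, remits, and fails a later course. Under the rule as written these children leave the analysis entirely, with the relapses and prescriptions from the time when they were steroid sensitive.

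Three things are at stake.

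- **Relapse rate.** If each relapse course is a further opportunity to meet the 8-week criterion, removal becomes more likely as the outcome count rises, and the analysed rate is too low.
- **Dose association.** If failure at 8 weeks also depends on the dose prescribed, removal depends on exposure and outcome together, and the rate ratio can be biased.
- **Objective 2.** The unit is the episode and the outcome is what the physician prescribed. Prescriptions made before resistance was known are the behaviour under study, yet they are dropped because of a later event.

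**Working it through.** **The plan's own figure.** Section 3.2 gives dose SD 8.85, mean dose 30.64 mg/m², base rate 1.68 per person-year, average follow-up 2 years, R² 0.2, two-sided α 0.05, N = 597 and a detectable rate ratio of 0.989 at 90% power. Take 1.68 as the rate at dose zero and the ratio as per 1 mg/m² (inferred), with b = ln 0.989 = −0.01106.

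- Expected relapses per child: m = 1.68 × 2 × exp(b × 30.64 + b² × 8.85²/2) = 2.406.
- Power = Φ(|b| × √(N(1 − R²) × m × SD²) − 1.960) = Φ(0.01106 × √(597 × 0.8 × 2.406 × 78.32) − 1.960) = Φ(3.318 − 1.960) = 0.913.
- The ratio detectable at exactly 90% power is 0.9893.

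The stated figure reproduces, so this point exposes no arithmetic error.

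**Inputs that must be assumed.** The protocol gives neither a frequency of late resistance nor a link between relapse count and resistance. The simulation uses:

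- relapse counts that are Poisson with mean 1.68 × follow-up × a gamma multiplier (mean 1, variance 0.5 or 1);
- follow-up uniform from 0.5 to 4 years (the maximum in section 3.2), repeated to 4.5 years (the 4-year enrolment plus 6 months in section 3.1);
- a chance q of being declared resistant at each relapse, so that P(removed) = 1 − (1 − q)^count;
- optionally, q multiplied by exp(−k × (dose − mean)), with k = 0 or ±0.05 per mg/m².

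The model is Poisson regression with log follow-up as offset.

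**Effect on the rate** (k = 0, follow-up 0.5–4 years):

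| q | Gamma variance | Children removed | Relapses/year in removed | Analysed rate, all → after exclusion |
|---|---|---|---|---|
| 0.5% | 0.5 | 1.9% | 2.9 | 1.68 → 1.65 |
| 0.5% | 1 | 1.9% | 3.7 | 1.68 → 1.64 |
| 2% | 0.5 | 7.0% | 2.8 | 1.68 → 1.58 |
| 2% | 1 | 7.0% | 3.6 | 1.68 → 1.51 |

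With follow-up to 4.5 years, removal is 2.1% to 7.8% and the analysed rate is 1.65 to 1.50. Adding dose dependence raises removal to at most 8.4%.

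**Effect on the rate ratio** (true value 1.000):

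- k = 0: it stays at 1.000.
- k = +0.05 (resistance less likely at higher dose): 1.001 at q = 0.5%, and 1.003–1.005 at q = 2%.
- k = −0.05 (more likely at higher dose): 0.999 at q = 0.5%, and 0.997–0.995 at q = 2%.

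The extremes are a little under half the stated detectable effect on the log scale: ln 0.995 / ln 0.989 = 0.45.

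**How much censoring recovers.** Keep late-resistant children and stop their follow-up when the resistant episode starts.

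- If the relapse that opens that episode is not counted, about a third to two fifths of the lost rate comes back.
- If it is counted and follow-up then stops, around 60% to two thirds comes back. For q = 2%, variance 1 and 0.5–4 years, the rate goes from 1.51 to 1.61, against 1.68 with no exclusion.
- The rate-ratio bias behaves alike. With k = +0.05 in that setting, 1.0052 becomes 1.0031 without the opening relapse and 1.0020 with it.

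**The case against.** The strongest defence is that *ultimately* has an innocent meaning. Children with a first presentation enrol before any steroid has been given, so their response cannot be known at entry and has to be classified later. Appendix Table 2 may separate initial from late resistance. Excluding resistant children also follows the declared target population, and section 3.2 already counts resistance within the 10% drop-out. This defence stands for children who never remit on their first course: they contribute no relapse and no steroid-sensitive history, and their exclusion is right. It does not cover children who enter at relapse, and the rule as written reaches them.

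A reader might infer that the highest-relapsing histories are in fact deleted preferentially. The documents do not support that. It follows only if each relapse carries its own chance of late resistance, which the simulation builds in and the protocol nowhere states. Nor does it describe the excluded group as a whole: if 8% were resistant from the start (an assumption), all excluded children together would average only about 0.6 to 1.6 relapses per year.

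A reader might also infer that the primary association is biased in a known direction. Without dose dependence it is not biased at all, and with it the sign follows an unknown relation.

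Finally, censoring and sensitivity analyses are often left to a statistical analysis plan, and one may exist. Here, however, the protocol itself fixes a whole-patient exclusion, so the wording to correct is in the protocol.

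**Conclusion.** The concern holds in a limited form. As written, the exclusion makes analysis membership depend on course after entry, and it discards valid steroid-sensitive follow-up in Objective 1 and valid prescriptions in Objective 2. That much rests on the text alone, subject to Appendix Table 2.

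The size is conditional. With an assumed 0.5–2% chance of late resistance per relapse, about 2–8% of children are lost and the analysed relapse rate is about 2% to 11% too low (1.65/1.68 = 0.98; 1.50/1.68 = 0.89). The dose rate ratio is affected only if late resistance also depends on dose, by up to about 0.005 in either direction. This is worth correcting before analysis, but it does not overturn the design or the stated detectable effect.

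**What to change.** In the exclusion criteria of section 3.1 and the analysis plans of sections 3.2 and 3.3:

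- Limit whole-patient exclusion to children who never remitted on their first course.
- Keep children with a documented initial remission. For relapse entrants the relapse itself implies one; confirm it by chart where available.
- Objective 1: count the relapse that opens the resistant episode, then censor follow-up and steroid exposure there. A child whose entry relapse is itself the resistant episode has no earlier prospective follow-up to contribute.
- Objective 2: keep all episodes before the resistant one.
- Report the present whole-patient exclusion as a sensitivity analysis.

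If Appendix Table 2 already confines resistance to the first course, say so in the exclusion criterion and state how later resistance is handled.

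The cost is a few sentences and some chart confirmation, which section 3.1 promises for relapse entrants only when records are available. These children stay in follow-up and each relapse is already dated, so no new data stream is needed. Censoring reduces the selection but does not remove it, and the report should say so.
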